As part of this study, it will be necessary to review the patient's medical history to ensure that they have no contraindications to neuraxial anesthesia or a quadratus lumborum block. This typically involves briefly looking through the patients medical record to check their medical history and lab values, and a face to face discussion with the patient prior to their cesarean delivery. All patients presenting for an elective cesarean delivery are also routinely given a paper form that reviews their medical history. All of this information will be reviewed both for their routine care and also for the purposes of this study. No additional information other than what is reviewed for routine care for an elective cesarean will need to be obtained as a result of this study. For participants receiving QLB, data summarizing the procedure including exactly what medication and dose was given will be placed in the UPMC/Pitt medical record ("Study Drug" for the local anesthetic will be noted, to maintain blinding). Following the cesarean delivery, some follow-up measures (e.g. oral and parenteral pain medications) may be gleaned and recorded as it is routinely documented in the medical record.

2.14.1 Will protected health information from a non-UPMC/Pitt HIPAA covered entity be obtained for research purposes or will research data be placed in the non-UPMC/Pitt medical record?

* No

I, [name], certify that any member of my research team accessing, reviewing and/or recording information from medical records have completed HIPAA Researchers Privacy Requirements (Formerly RPF Module 6) training. The HIPAA certificates must be available for review if audited but do not need to be uploaded into this OSIRIS application.

* Yes

2.14.2

Are you requesting a waiver of the requirement to obtain written HIPAA authorization for the collection of the PHI?

* No

[reviewer notes-]**2.15 Does this research study involve the long-term storage (banking) of biological specimens?**

* No

[reviewer notes-]**2.16 Will research participants be asked to provide information about their family members or acquaintances?**

* No

[reviewer notes-]**2.17 What are the main outcome variables that will be evaluated in this study?**

The outcome measures that will be assessed and evaluated in all three groups include:

- VAS pain scores at rest and with movement (VAS pain score with movement at 24 hours will be the primary outcome)

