- Time to first request for PRN oral or parenteral opioid
- Total opioid analgesics required throughout hospital stay
- Presence/absence of sedation, itching, and nausea/vomiting
- Vital signs - respiratory rate (RR), and oxygen saturation (SpO₂)
- Signs of local anesthetic toxicity (e.g., perioral numbness, ringing in the ears, or metallic taste in the mouth, other non-specific neurological symptoms) within 4 hours of block (assessed at 15min, 30 min, 45 min, 1 hour and 4 hours by nursing or study personnel)
- Breastfeeding success and quality

The primary outcome will be measured at baseline (entry to post-anesthesia care unit, and immediately after QLB) and at 1 hour, 4 hours, 24 hours, and 48 hours following completion of the QLB. Follow-up will occur in the recovery room and in patient's rooms.

2.18 Describe the statistical approaches that will be used to analyze the study data.

* Addressed below:

The primary outcome is the mean numeric rating scale (NRS) pain scores with activity at 24 hours after completion of the quadratus lumborum block. The primary outcome will be compared between groups using the two-tailed unpaired Student t-test. Interval and ordinal data will be compared between groups using the two-tailed Student's t-test or the Mann-Whitney U-test after testing for normal distribution. Categorical data will be compared using a Chi-Square statistic or the Fisher's exact test.

We will apply Bonferroni correction for multiple comparisons. The time-to-first-supplemental opioid analgesic request will be compared by Cox proportional hazard modeling. Subjects who do not request additional analgesia will be censored at the time of delivery. $P < 0.05$ will be used to reject the null hypothesis.

[reviewer notes-]

2.19

Will this research be conducted in (a) a foreign country and/or (b) at a site (e.g., Navajo Nation) where the cultural background of the subject population differs substantially from that of Pittsburgh and its surrounding communities?

* No

Note that copies of training records, licenses, certificates should be maintained in the study regulatory binder and are subject to audit by the Research Conduct and Compliance Office (RCCO).

In addition, individuals planning to conduct human subject research outside the United States must complete an optional module on the CITI training website: International Studies. [Click here](#) to access the instruction sheet for accessing optional CITI modules.

[reviewer notes-]

2.21

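### Bonferroni is named for an undefined set of comparisons; once the set is defined, Holm's procedure gives the same error control and never rejects less, for a modest gain

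*Protocol*

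**What the plan says.** Protocol section 2.18 gives the primary outcome its own test: "The primary outcome will be compared between groups using the two-tailed unpaired Student t-test". Other measured outcomes follow a general rule: "Interval and ordinal data will be compared between groups using the two-tailed Student's t-test or the Mann-Whitney U-test after testing for normal distribution". Categorical outcomes get a chi-square or Fisher test. For the opioid-request outcome, "The time-to-first-supplemental opioid analgesic request will be compared by Cox proportional hazard modeling". Multiplicity is covered by "We will apply Bonferroni correction for multiple comparisons", and the paragraph ends by stating that a P value below 0.05 "will be used to reject the null hypothesis", without saying whether that P value is taken before or after correction.

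Section 2.17 lists the outcomes: "VAS pain scores at rest and with movement", time to first opioid request, total opioid use, sedation, itching, nausea or vomiting, vital signs, signs of local anesthetic toxicity, and breastfeeding. Pain with movement at 24 hours is marked as primary; nothing else is labelled secondary efficacy or safety. Scores are taken at baseline and "at 1 hour, 4 hours, 24 hours, and 48 hours following completion of the QLB".

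The SAP repeats the primary outcome and the sample-size argument. It does not mention secondary outcomes or multiplicity.

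**The concern.** The multiplicity sentence cannot be carried out as it stands, because Bonferroni needs a number of tests and the plan gives none. Whoever fills that gap must also decide whether the primary outcome is inside the family, and this affects the main test.

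Once a family is set, single-step Bonferroni holds every test to the strictest threshold. Holm relaxes the threshold after each rejection and needs no extra assumption. Whether the block also affects pain at rest, pain at other times and opioid use depends on outcomes that would sit in this family. A method that can only match or improve on the planned one, at the same error rate, is therefore worth naming when the sentence is rewritten.

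**Working it through.** **What the correction can apply to.** The protocol abstract and sections 2.6 and 3.11 describe two randomized groups, so each outcome has one between-group comparison. Sections 2.6 and 2.17 still introduce the outcomes with "The outcome measures that will be assessed and evaluated in all three groups include", which conflicts with that design. With two groups there are no several pairwise group comparisons to correct, which leaves several outcomes and several times.

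**Inputs.** From section 3.12 and the SAP: 26 completers per group, SD 2.22, and group values of 4 and 2, a difference of 2. The standardized effect is 2/2.22 = 0.90. The plan gives no adjusted alpha and no power for any outcome but the primary, so there is no secondary figure to reproduce.

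**Family size is an assumption.** If pain at rest follows the same schedule as pain with movement, there are 2 × 4 = 8 pain scores after baseline, less the primary = 7. Adding 2 opioid outcomes, 3 side effects and breastfeeding gives 13. Without the side effects it is 10. A family as small as 3 (pain at rest at 24 h and the two opioid outcomes) is also defensible.

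**Why Holm never rejects less.** Order the m P values from smallest to largest. Bonferroni compares each with 0.05/m. Holm compares the k-th with 0.05/(m − k + 1) and stops at the first failure. Since 0.05/(m − k + 1) ≥ 0.05/m for every k, any P value that passes Bonferroni passes Holm. For m = 13 the Holm thresholds are 0.05/13 = 0.0038, 0.05/12 = 0.0042, 0.05/11 = 0.0045, and so on up to 0.05. The first threshold is the same under both methods, so the chance of finding anything at all hardly moves.

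**Bonferroni is valid.** For independent tests, 1 − (1 − 0.05/m)^m = 4.92% at m = 3 and 4.89% at m = 13.

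**Power under Bonferroni, m = 13, normal approximation.** The expected test statistic is 0.90 × √(26/2) = 3.25, and the critical value at two-sided 0.05/13 is 2.89. Power is Φ(3.25 − 2.89) = Φ(0.36), about 64%.

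**Holm against Bonferroni, by simulation.** Normal test statistics, 26 per group, effect 0.9 SD, correlation 0.4 between tests; average power per real effect:

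| Tests in family | Real effects | Bonferroni | Holm | Gain (points) |
|---|---|---|---|---|
| 13 | 1 | 64.1% | 64.2% | 0.1 |
| 13 | 7 | 64% | 68% | 4 |
| 11 | 9 | 66% | 74% | 8 |
| 6 | 5 | 73% | 80% | 7 |

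**Sensitivity.** At zero correlation with about half the effects real, the figures are 69.7% to 73.3% for m = 8 and 64.1% to 67.6% for m = 13. The extreme case, all 13 effects real and uncorrelated, is 64.0% to 78.9%. At 0.5 SD the gain is 0 to about 5 points. With 13 tests, 6 real effects of 0.9 SD and correlation 0.5, the chance of at least one true finding is 93.3% under both methods. Holm rejected everything Bonferroni rejected in every simulated trial, and its family-wise error was at most 4.7%.

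**If the primary were in the family.** Its power at 26 per group (normal approximation) would fall from 90.1% at 0.05 to 80.4% at m = 3, 69.6% at m = 8 and 64.0% at m = 13. The sample-size calculation uses 0.05 without adjustment, which fits testing the primary alone.

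**The case against.** The strongest reply is that Bonferroni is a legitimate choice. It controls the error rate and gives simultaneous confidence intervals in one step. Only the primary outcome is powered, and if it is tested alone the main conclusion is the same under either method. The documents give no effect sizes, correlations or count of real effects for the other outcomes, so no particular loss can be attributed to the plan. All of this stands, and it limits the point to an optional improvement.

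Three stronger readings are tempting and are not supported.

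- **That the plan subjects its secondary efficacy outcomes to Bonferroni as a stated family.** Section 2.18 defines no family, and no outcome carries that label. The two-group design implies several outcomes and times, but not which ones.
- **That real effects will be missed for no gain.** A reader might compare 89% power for a 2-point difference at 0.05 with 54% at 0.05/19 (19 tests assumed). That is the price of adjusting at all, not of choosing Bonferroni over Holm. Bonferroni also has the advantage of simpler intervals.
- **That the pain scores must be pooled in a repeated-measures contrast.** For a constant 1.5-point effect over 4, 24 and 48 h, pooling at 0.05/6 raises power from 39% to 60% (within-woman correlation 0.5). No passage supports a constant effect. If it faded as 2, 1, 0 points, the mean effect would be 1 point with SD 2.22 × √((1 + 2 × 0.5)/3) = 1.81. Pooled power at 0.05/6 would be 24%, against 54% for the 4 h test alone even at 0.05/19. A movement contrast that includes 24 h would also re-use the primary outcome. Pooling is a trade-off, not a requirement.

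**Conclusion.** The point holds in limited form. The multiplicity sentence names a valid but single-step method for a family it does not define. Holm dominates it in rejections at the same family-wise error under any dependence; that is a mathematical fact and needs no trial assumption.

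The size of the benefit does need assumptions. With 26 per arm, 0.9 SD effects and correlation 0.4, it is about 0 points of average power with one real effect, 3 to 4 with about half real, and 7 to 8 with nearly all real. It is smaller for smaller effects and larger only if every effect is real. The trial's main conclusion is unaffected provided the primary is tested alone. The change is worth considering because the sentence has to be completed anyway.

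**What to change.** Replace the multiplicity sentence in Protocol 2.18, and add the same text to the SAP: *The primary outcome is tested alone at two-sided 0.05; the listed secondary efficacy outcomes are tested with Holm's procedure at family-wise 0.05.* Add the list itself, with each outcome and time point, so that the number of tests is fixed before unblinding. Say that the closing 0.05 criterion applies to the primary P value and to Holm-adjusted secondary P values. Report other outcomes descriptively or as unadjusted, and label them so.

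Holm works on any valid P values, so the planned t, Mann-Whitney, chi-square, Fisher and Cox analyses can stay. The cost is a few lines of text and code, with no loss in error control. The one drawback is that matching simultaneous intervals are less simple than under Bonferroni; ordinary 95% intervals, labelled as unadjusted, can be shown beside the adjusted P values. A repeated-measures summary of pain may be added as an option but is not part of this change.

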We will determine if the quadratus lumborum block (QLB) provides superior analgesia to patients following cesarean delivery compared to the current standard of care, multi-modal analgesia (i.e., ITM and scheduled post-operative non-opioid oral analgesics, with oral opioid analgesics reserved for breakthrough pain).

We will measure side-effects associated with each strategy: standard of care (ITM + care described above, plus sham QLB with saline), and standard of care plus true QLB.

We will measure and model economic ramifications associated with each strategy, modeling factors including drug costs, procedure costs, costs associated with length of stay and re-admissions.

1.3 Background: Briefly describe previous findings or observations that provide the background leading to this proposal.

The quadratus lumborum block (QLB) is similar to the transversus abdominis plane (TAP) block, but differs slightly in regards to the location where local anesthetic is injected. Because of the more posterior location of the QLB, it theoretically confers greater safety due to enhanced visualization (1). The TAP block has been studied extensively for post-cesarean delivery pain, consistently showing that it is not superior to ITM for post-operative analgesia, but that it may have a role in patients with breakthrough pain despite the use of ITM, or in patients who were unable to receive it (e.g. general anesthesia for cesarean, contraindications to neuraxial morphine). ITM is superior to TAP alone for post-cesarean analgesia, but it is associated with a dose-dependent increased risk for opioid related side effects (2,4,5). In 2015, Blanco et. al. published a study specifically using the QLB for postoperative pain after cesarean delivery (1). In this study, they compared a true QLB to a sham QLB all in patients who did not receive ITM, and found that the QLB provided improved pain control and decreased the need for post-operative opioids. Another study in 2016 demonstrated that the QLB is superior to the TAP block in regards to decreasing post-operative pain following c-section (3). Unfortunately, neither study compared the QLB to ITM (part of the current gold standard for post-cesarean delivery pain, multimodal analgesia).

References
(see supporting documentation)

1.4 Significance: Why is it important that this research be conducted? What gaps in existing information or knowledge is this research intended to fill?

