3.8 Does this research study involve neonates of uncertain viability or nonviable neonates?

- * No

[reviewer notes.]

3.9 Fetal Tissues: Does this research involve the use of fetal tissues or organs?

- * No

[reviewer notes-]

--->

3.10

What is the total number of subjects to be studied at this site, including subjects to be screened for eligibility?

Note: The number below is calculated by summing the data entered in question 3.11. Any additions or changes to the values entered in 3.11 will be reflected in 3.10.

* 60

3.11

Identify each of the disease or condition specific subgroups (include healthy volunteers, if applicable) that will be studied.

Click on the "Add" button and specify for each subgroup:

- 1) **how many subjects will undergo research related procedures at this site; and**
- 2) **if applicable, how many subjects will be required to undergo screening procedures (e.g., blood work, EKG, x-rays, etc.) to establish eligibility. Do Not include subjects who will undergo preliminary telephone screening.**

*

Subgroup	Number to undergo research procedures	Number to undergo screening procedures
Control (ITM plus sham View QLB)	26	30
Experimental (ITM plus View b upl'vacai'ne QLB)	26	30

3.12

Provide a statistical justification for the total number of subjects to be enrolled into this research study at the multicenter sites or this site.

* Described below:

The primary outcome is the mean numeric rating scale (NRS) pain scores with activity at 24 hours after completion of the quadratus lumborum block. Previous work comparing dynamic pain outcomes among women undergoing cesarean delivery with and without quadratus lumborum block 1 reported median [IQR] pain scores at 24 hours of 2[0-3] in the intervention group and 4[2-5] in the control group. Mean and standard deviation were estimated from this data using mean=median and $SD = IQR/1.35$. For 2 groups, a total sample of 60 subjects (26 in each group completed) is estimated to achieve 80% power to detect differences among the NRS means versus the alternative of equal means using an F test with a 0.05 significance level. The size of the variation in the means represented by the standard deviation is assumed to be 1.00, with a common standard deviation within a group of 2.22. To account for subject dropout and/or ineligibility, 60 subjects will be screened for randomization into 2 groups, with 30 subjects to be screened for each group.

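### Side effects and local anesthetic toxicity get significance tests only, with an undefined Bonferroni family and no planned interval, at a sample size that will usually miss rare or modest harm

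*Protocol*

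**What the plan says.** Protocol section 1.2 sets the aim: "We will measure side-effects associated with each strategy: standard of care" with sham block, against the same care plus the true block. It attaches no hypothesis, margin or power to this aim.

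Section 2.17 lists sedation, itching and nausea/vomiting as present or absent, and also "Signs of local anesthetic toxicity (e.g., perioral numbness, ringing in the ears, or metallic taste in the mouth, other non-specific neurological symptoms". Section 2.6 rates the three named toxicity signs as present or absent, and additionally grades pruritus and nausea from 0 to 3.

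Section 2.18 gives the analysis: "Categorical data will be compared using a Chi-Square statistic or the Fisher's exact test". Ordinal data get a t-test or Mann-Whitney test. Then comes "We will apply Bonferroni correction for multiple comparisons", with no family and no number of tests, and a rejection threshold of P<0.05. No estimate with an interval is planned for any safety outcome. The SAP covers only the primary outcome and the sample size.

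The numbers come from section 3.12: "a total sample of 60 subjects (26 in each group completed) is estimated to achieve 80% power", "using an F test with a 0.05 significance level".

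**The concern.** The trial asks whether a bupivacaine block is worth adding to analgesia that already works, so any gain in pain has to be weighed against harm. An aim to measure harm calls for an estimate and its precision, but the stated rule yields only a P value. If the tests have little power, most real differences in side effects or toxicity will come out as not significant, and nothing in the plan obliges the report to show how large a harm the data still allow. Any Bonferroni divisor that covers safety raises the bar further: each added safety outcome makes a true harm harder to declare.

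**Working it through.** **Inputs.** From section 3.12: 26 completers per arm, 30 per arm before dropout. From section 2.18: two-sided tests, threshold 0.05. The documents give no event rates and no number of tests m. I assume the rates shown below, and m = 6 (three side effects plus three named toxicity signs), so 0.05/6 = 0.0083.

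**The plan's own figure.** Section 3.12 sizes the primary outcome only. An SD of the means of 1.00 in two groups is a difference of 2.0; with a within-group SD of 2.22 and 26 per group, the noncentrality is (2.0/2.22)·√(26/2) = 3.25, which gives 89% power, and 21 per group would give 80%. The stated 80% at 26 therefore does not reproduce. That is a separate matter: this point needs only n = 26. No figure is stated for side effects or toxicity.

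**Events needed against zero.** For k v 0 events with 26 per arm, the two-sided Fisher p is 2·C(26,k)/C(52,k).
- k = 5: 2 × 65,780/2,598,960 = 0.051
- k = 6: 2 × 230,230/20,358,520 = 0.023
- k = 8: 2 × 1,562,275/752,538,150 = 0.0042

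So 6 v 0 (23% v 0%) is needed at 0.05. At 0.0083 it takes 8 v 0 (31% v 0%), since 7 v 0 gives 0.0098.

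**Miss rates at 26 per arm.** Miss rate = 1 − Σ P(a)·P(b) over all tables with p < 0.05/m, where a and b are binomial counts. For example, at 10% v 0%, P(at least 6 of 26) = 0.040, so 96.0% are missed; P(at least 8) = 0.003, so 99.7% are missed.

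| Assumed rates | Fisher, 0.05 | Fisher, m=6 | Chi-square, 0.05 | Chi-square, m=6 |
|---|---|---|---|---|
| 10% v 0% | 96% | 99.7% | 74% | 99% |
| 20% v 0% | 58% | 87% | 21% | 75% |
| 30% v 10% | 68% | 90% | 53% | 83% |
| 60% v 40% | 79% | 93% | 72% | 89% |
| 50% v 10% | 15% | 37% | 8% | 26% |
| 70% v 30% | 24% | 50% | 17% | 38% |

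Chi-square here is without continuity correction. At 20% v 0% the expected event count is 2.6 per arm (26 × 0.20 / 2), where Fisher is the usual choice, but section 2.18 gives no rule for choosing between the tests.

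**Sensitivity.** With m = 3, Fisher misses 99%, 75%, 84% and 89% in the first four rows. With 30 per arm and m = 6 it misses 99%, 76%, 85% and 92%.

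**Graded scales.** In a simulated Mann-Whitney test on the 0-3 scale, an assumed shift from 70/20/7/3% to 50/25/15/10% (none/mild/moderate/severe) is missed 64% of the time at 0.05 and 86% with m = 6. A large shift, from 60/25/10/5% to 25/30/25/20%, is missed 18% and 42%.

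**What an interval would show.**
- 0 of 26: exact upper limit 1 − 0.025^(1/26) = 13.2% (two-sided 95%), or 1 − 0.05^(1/26) = 10.9% (one-sided).
- 3/26 v 0/26: Fisher p = 2 × 2,600/22,100 = 0.24, while the Newcombe difference is +11.5 points (−3.4 to +29.0).
- 8/26 v 5/26: +11.5 points (−11.9 to +33.5).

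**The case against.** Several stronger readings are tempting, and the documents do not support them.

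- *The trial will report no difference in harm.* Neither document says that a non-significant result will be read that way. Aim 2 speaks only of measuring. Silence on intervals in a short form field is not a plan to withhold estimates.
- *Bonferroni is certain to cover safety.* The sentence names no family. It could mean the pain time points, the secondary outcomes or everything. The defect is that the family is undefined and safety is not exempted.
- *Bonferroni is the cause.* At 10% v 0%, Fisher misses 96% with no correction at all. Sample size does most of the damage, and exempting safety would barely help with rare toxicity. Reporting intervals is the part of the fix that matters there.
- *Harm will almost always be missed.* This fits rare toxicity under Fisher. It does not fit 50% v 10%, which is missed 15% to 37% of the time, or a large ordinal shift. Unadjusted chi-square would usually find even 20% v 0%.
- *Every safety outcome should leave the correction.* The abstract lists nausea, vomiting and pruritus as effects of intrathecal morphine, which both arms receive. If the block spares opioid, these outcomes could be claimed as benefits, and uncorrected testing would then inflate false claims in its favour.

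It is also fair to say that safety is not left to P values alone. Toxicity signs are checked at five times within 4 hours, and section 5.13 provides daily adverse-event review. That is oversight of individual patients, however, and it supplies no comparison between arms. What stands against these objections is the missing estimate and the undefined family.

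**Conclusion.** The point holds in limited form. The between-arm safety analysis consists of tests alone, under a correction whose scope is unstated, and no interval is planned in either document. At 26 per arm these tests will usually miss rare toxicity, and with Fisher they will usually miss differences of up to about 20 points: 58% to 96% missed unadjusted in the first four scenarios, 87% or more if six tests are corrected for. Uncorrected chi-square misses fewer, with 20% v 0% the clear exception. Zero toxicity events in the bupivacaine arm would still be compatible with a true rate of 13.2%.

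All miss rates depend on assumed event rates, and the corrected ones on an assumed m; the 13.2% bound depends only on n = 26. The primary result is not affected. This is a cheap improvement that changes what the trial can say about harm.

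**What to change.** In section 2.18 and the SAP:

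1. Name the Bonferroni family and the number of tests in it.
2. Exclude the toxicity signs, and any comparison that will be read as harm. Keep the correction for any claim that the block reduces nausea, itching or sedation.
3. For each binary safety outcome, report counts per arm and the risk difference with an unadjusted 95% confidence interval (Newcombe). Where an arm has no events, add the exact upper bound.
4. State that a non-significant P value is not evidence of no harm.

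This costs a few sentences, with no new data or patients. The small downside is a higher chance of a false safety signal, and intervals that will be visibly wide at this sample size.
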